8.5 Cohort dimension

Expected cohort dimension is of 33 patients that is the number of patients followed at the Neurological Unit in the last 10 years. Statistical analysis will be based on generalized linear regression models, suitable both for continuous variables both for independent ones. Variables with a nonlinear distribution will be used only in logarithmic scale. Only data corresponding to yearly visit (at least two data in two years) will be used for the linear correlation analysis and in multivariate correlation models. Furthermore, to verify the accuracy of clinical variables in

describing the evolution of the dystrophy, variables will be coupled and compared by a bivariate analysis.

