8.1.1 Primary endpoints

To describe the natural history of the LGMD 2E

To define of the clinical variables that more strongly relate with the evolution of the disease

To identify any possible correlation between variables

To identify any possible correlation between variables and clinical outcomes

To identify any possible correlation between phenotype and genotype

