8.7 Data analysis

Analysis will be performed using generalized linear regression models suitable both for continuous variables both for independent ones. Variables with a nonlinear distribution will be transformed in logarithmic scale before the analysis to be performed. For any analysis data will be divided according to the age of the patient at the moment of the evaluation. Data will be analyzed with linear correlation both compared to the variable age both in bivariate models and multivariate models. Results obtained will be adjusted for confounding factors not related to muscular dystrophy.

Data of included patients will be globally studied and divided in two groups homogeneous for genotype.

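### Protocol 8.5 and 8.7 require repeated yearly values but analyse them by linear correlation and generalized linear regression with no term for the patient, so with visits as rows false associations are declared too often

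*Protocol*

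**What the plan says.** Protocol section 8.5 expects 33 patients and sets the data for the correlation work: "Only data corresponding to yearly visit (at least two data in two years) will be used for the linear correlation analysis", and likewise for the multivariate correlation models. A separate sentence there adds that "variables will be coupled and compared by a bivariate analysis".

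Section 8.7 sets the method. "Analysis will be performed using generalized linear regression models suitable both for continuous variables both for independent ones". Age belongs to the visit: "For any analysis data will be divided according to the age of the patient at the moment of the evaluation". Then: "Data will be analyzed with linear correlation both compared to the variable age both in bivariate models and multivariate models". For genotype: "Data of included patients will be globally studied and divided in two groups homogeneous for genotype". The one adjustment named is this: "Results obtained will be adjusted for confounding factors not related to muscular dystrophy".

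Section 8.1.1 lists these associations as primary endpoints, for example "To identify any possible correlation between phenotype and genotype", and section 8.7.1 repeats the correlations of variables with progression and with each other as the primary analysis. Section 8.2.2 admits both adults and minors. Section 8.3 puts a patient code in the data file.

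The protocol mentions no random effect, GEE, clustered standard error, per-patient slope or rule of one value per patient.

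**The concern.** Ordinary regression and linear correlation treat each row as a separate piece of evidence. Yearly measurements of one person with a slowly progressive dystrophy resemble each other, so a second or fifth visit adds less than a new patient would. Where the covariate differs mainly between patients, the naive standard error is then too small. Genotype never changes within a patient. In a cohort of minors and adults, most of the spread in age also lies between patients.

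A single coefficient for age has a second problem: it blends how older patients differ from younger ones with how a given patient changes over time. Only the second is progression in the ordinary sense, and a natural history study needs to see the two apart.

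At stake is which variables are reported as tracking the disease. Section 8.7.2 uses the results to choose what to follow and which examinations to call useless, and section 8.9 shows that statistical significance is a goal.

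**Working it through.** **No planned figure to reproduce.** The 33 patients are a count of those followed over ten years, not the result of a power calculation.

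**Inputs from the protocol:** 33 patients; at least two yearly values (8.5); age at evaluation (8.7); two genotype groups (8.7); adults and minors (8.2.2).

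**Assumptions, because the protocol does not give them:** two-sided 5% level; m = 2 values per patient (the stated minimum) or m = 5; intraclass correlation (ICC) 0.5 to 0.8; genotype groups of 17 and 16; first-visit age SD 10 years; visits entered as rows.

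**Step 1. Covariate that is constant within a patient (genotype).** Design effect DE = 1 + (m − 1) × ICC. Ratio of naive to true standard error = 1/√DE. Actual error rate = 2 × (1 − Φ(1.96/√DE)). Effective rows = 33m/DE.

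| m | ICC | DE | SE ratio | Effective rows | Error rate |
|---|---|---|---|---|---|
| 2 | 0.5 | 1.5 | 0.82 | 44 of 66 | 11% |
| 2 | 0.8 | 1.8 | 0.75 | 37 of 66 | 14% |
| 5 | 0.5 | 3.0 | 0.58 | 55 of 165 | 26% |
| 5 | 0.8 | 4.2 | 0.49 | 39 of 165 | 34% |

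**Step 2. Two unrelated variables, both repeated, with the same ICC.** Here DE = 1 + (m − 1) × ICC². For m = 2 this is 1.25 to 1.64, giving 8-13%. For m = 5 it is 2.00 to 3.56, giving 17-30%.

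**Step 3. Simulation with no true association, visits as rows.** Ranges cover repeated runs under the assumptions above.

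| | m = 2 | m = 5 |
|---|---|---|
| Genotype | 11-15% | 26-36% |
| Age | 11-16% | 25-35% |
| Pairs of variables | 8-13% | 16-32% |

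Overall this is about 8-16% at two values and 16-36% at five. Relative to 5%, that is 8/5 = 1.6 times up to 36/5, or about 7 times.

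**Step 4. Sensitivity.**
- Unequal visits (11 patients each with 2, 3 and 5 values, 110 rows): genotype 21-30%, age 20-28%, pairs 12-25%.
- Yes/no outcome by logistic regression: 8-12% at two values, 19-29% at five.
- Age SD varied from 5 to 15 years: age 11-16% at two values, 25-35% at five.
- All patients starting at the same age: the age test becomes conservative, below 1%. The age result therefore depends on patients differing in age.

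**Step 5. Does respecting the patient restore the level?** Patient means give about 5% for genotype, for between-patient age and for pairs. For genotype, patient-clustered standard errors give 4.7-5.7%. For between-patient age, plain clustered errors still give 7-8%, and a jackknife-type correction brings this to 5.1-6.6%. Per-patient slopes give 4.7-5.2% for within-patient age.

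**The case against.** The strongest reply is that the protocol never says visits are independent rows, and that handling of within-patient correlation is commonly left to a statistical analysis plan. Generalized linear regression is a broad class, and GEE or clustered errors are ways of fitting and testing it. The two-value minimum could be an eligibility filter for per-patient change. Division by age could mean bands that each hold about one value per patient.

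Part of this stands: rows-as-visits is the natural reading, not a literal statement. But the text describes neither alternative. No band width is given, and a band wider than one year can hold several values of one patient. Nor is this a protocol silent on method. It makes repeated values a requirement, names regression and linear correlation for them, and names an adjustment that is not a patient effect.

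The genotype and pairing objection also stands in part. The yearly-visit rule is attached to the linear correlation and the multivariate models. The pairing sentence follows separately, and the genotype sentence could mean repeating the analyses within each group. A reader might infer that every genotype and pairwise result is inflated. The protocol does not support that: these analyses are affected only where they use repeated values.

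A reader might also infer that the clinical outcomes are compromised. Section 8.4 defines them as ages at loss of ambulation and at introduction of cardiac drugs or respiratory support, one value per patient for each, so they are not.

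Finally, this is a small retrospective study, and section 8.9 admits that the data may be too few for reliable analysis. That caveat concerns too little information. Counting visits as independent evidence makes the information look larger than it is.

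**Conclusion.** The point holds as a stated method that does not fit its stated data, and it should be fixed. It is firmest for the correlation of repeated variables with age at evaluation, which the text ties directly to the yearly values.

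The size rests on the assumed level, visit numbers and ICC, on visits entering as rows and, for age, on patients differing widely in age, which fits a cohort of adults and minors. The upward direction held in every scenario run with such an age spread; the exact rate cannot be read from the protocol. A reader might round the effect to at least a doubling of false positives. That is too strong, because pairs of variables, and yes/no outcomes, start at about 8% with two values.

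**What to change.** In sections 8.5 and 8.7, state that:

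- variables measured at more than one visit are analysed with a patient random effect, or with GEE or patient-clustered standard errors with a small-sample correction;
- age is split into the patient's mean or first-visit age and the deviation from it, so that between-patient and within-patient effects are reported separately;
- two repeated variables are related through patient-level means or slopes, or by a model that separates the two levels, not by a pooled correlation.

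If the two-value rule is only an eligibility filter, or age bands with one value per patient are intended, say so.

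**Cost.** A few sentences and no new data, since the patient code and age are already collected. Intervals for between-patient effects widen by √DE: about 1.2-1.3 times at two values per patient and 1.7-2.0 times at five. Fewer associations will be significant.

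Two practical limits apply. With 33 patients the small-sample correction matters. A random slope may not be estimable with two values per patient, but leaving it out is not harmless: with an assumed between-patient slope SD of 0.2 outcome SDs per year, a random-intercept-only test of within-patient age rejects 12-16% at five values. Per-patient slopes or clustered errors stay at 4-6% and are the fallback.

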8.2 Setting

Patients followed by the ambulatory of neuromuscular disorders of Centro Dino Ferrari, Padiglione Monteggia of Fondazione IRCCS Ca' Granda Ospedale Maggiore Policlinico (Unit of Neurology), will be recruited during the ordinary follow up routine or will be reached out to participate to this study. Furthermore, thank to the sponsorship of Gruppo familiari beta sarcoglicanopatie (GFB), more patients that are in the network of this association will be reached out from the PI of the study and eventually included. Data will be provided by patients themselves during the visit at the room number 17 of Padiglione Monteggia of Fondazione IRCCS Ca' Granda Ospedale Maggiore Policlinico (Unit of Neurology). If the patients won't be able to move and will be interested in participating to the study a collaborator of the main researcher will reach the patients at his residence to recruit him. Main source of data will be the clinical chart of the patient and all his clinical documents assessing any operation, ascertain, visits performer through the years until this moment. Main centre will be the Fondazione IRCCS Ca' Granda Ospedale Maggiore Policlinico (Unit of Neurology). Data collection will last six months and later data will be studied.

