8.2.1 Study population

Studied population. The association GFB (GRUPPO FAMILIARI BETA-SARCOGLICANOPATIE) is a group of families of patients affected by beta-sarcoglycanopathy and other muscular dystrophies. This association has been created by few families resident in Lombardia and now it includes people from all over Italy. The study will be sponsored by GFB that will inform its associated about this study. Patients interested in participating to the study will reach out the PI of the study to be eventually included.

Furthermore, patients affected by LGMD 2E followed at the Fondazione IRCCS Ca' Granda Ospedale Maggiore Policlinico (Unit of Neurology) and that have previously signed an informed consent for the use of their data for scientific research will be included. Data from this second group of patients will already be available in databases created in our hospital for previous scientific researches.

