8.2.4 Patient participation

Patients might be asked to give to their physician their clinical charts in order to evaluate the visits and investigations performed through the years, also in other hospitals.

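### The yearly-visit filter in 8.5 drops single and widely spaced values from the correlation and multivariate models, which costs precision in a small cohort and selects by follow-up pattern

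*Protocol*

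**What the plan says.** Protocol 8.5 gives the cohort size as a head count: "Expected cohort dimension is of 33 patients that is the number of patients followed at the Neurological Unit in the last 10 years". It then sets a data rule: "Only data corresponding to yearly visit (at least two data in two years) will be used for the linear correlation analysis". The sentence continues to the multivariate correlation models, and a separate sentence describes a bivariate comparison of the variables.

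Protocol 8.7 makes linear correlation the core method: "Data will be analyzed with linear correlation both compared to the variable age both in bivariate models and multivariate models". It also groups data by the patient's age at each evaluation and splits the cohort into two genotype groups.

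The data are retrospective (8.1, 8.3). Patients may hand over charts "in order to evaluate the visits and investigations performed through the years, also in other hospitals" (8.2.4). Recruitment also draws on a patient association, of which 8.2.1 says "now it includes people from all over Italy". Eligibility needs only a genetic diagnosis and consent (8.2.2, 8.2.3), with no minimum follow-up.

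Clinical outcomes in 8.4 are ages at loss of ambulation and at the start of cardiac or respiratory support. They are read from the chart with no yearly-visit condition. Section 8.9 names scarcity of data as a limitation and does not mention the filter. The protocol gives no reason for the filter, no analysis of all data, and no comparison of data kept with data dropped.

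**The concern.** The study does not control when its patients were seen. Charts built up in routine care, some of them elsewhere, can be irregular, and nothing at entry requires regular follow-up. The protocol admits such patients and then withholds from its main models whatever fails a visit-pattern rule.

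Regular spacing is not needed for these analyses. Each value carries an age at evaluation, so a value taken at an odd interval still shows where that patient stood at that age.

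Two things are at stake. The first is precision, in a study whose own stated limitation is too few data and which divides its cohort again by genotype. The second is representativeness: the rule selects by how patients were followed. If that is related to how fast they progress, the filtered correlations describe a different group from the one recruited.

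**Working it through.** **Stated figure.** The 33 in 8.5 is a count of patients followed, not the result of a power calculation, so there is nothing to reproduce. It is not reduced for losses to the filter.

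**What the rule removes.** The phrase in brackets can be read in several ways:

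- It may apply per patient or per variable.
- It may require one value in each of two years, or any two values within two years.
- It may keep only values from yearly visits, or keep all values of a patient who meets the minimum.

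A patient or variable with only one value fails on every reading. So do values spaced so widely that no two fall within two years. Values taken off schedule are lost only on the stricter reading.

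**Precision.** Inputs: 33 patients (8.5); share kept, assumed at 60% to 80% because the protocol gives no visit frequencies. If dropped patients carry as much information as kept ones, the standard-error ratio is 1/√(share kept).

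- 80% kept: 33 × 0.80 = 26.4, so 26 patients; 1/√0.80 = 1.12.
- 70% kept: 33 × 0.70 = 23.1, so 23 patients; 1/√0.70 = 1.20.
- 60% kept: 33 × 0.60 = 19.8, so 20 patients; 1/√0.60 = 1.29.

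This gives a rise of 12% to 29%. It is an upper range, suited to cohort-level correlations. A patient with one value says nothing directly about within-patient change, so the loss for slopes is smaller.

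**What this does to one correlation.** Assumptions: r = 0.5, one value per patient, two-sided 5% level, 80% power. Fisher z interval: tanh(atanh(r) ± 1.96/√(n − 3)). Smallest detectable r: tanh((1.96 + 0.84)/√(n − 3)).

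| Patients | 95% interval at r = 0.5 | Smallest detectable r |
|---|---|---|
| 33 | 0.19 to 0.72 | 0.47 |
| 26 | 0.14 to 0.74 | 0.53 |
| 20 | 0.07 to 0.77 | 0.59 |

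**Possible selection bias.** Assumption: progression rate is standard normal across patients, and the log-odds of passing the filter are a + b·x, where x is the rate in SD units and b = ln(OR). The constant a is set to give the assumed share kept. The shift is the mean of x among those kept, E[x·p(x)]/E[p(x)].

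- OR 1 (follow-up unrelated to progression): shift 0.
- OR 1.5 per SD, 80% kept: shift 0.08 SD.
- OR 3 per SD, 60% kept: shift 0.35 SD.

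The sign depends on whether faster or slower decliners were seen more regularly, which the protocol does not tell us.

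**The case against.** The case for leaving the rule alone has four parts.

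**Reach.** The filter covers named analyses only. Nobody is excluded from the study, and the outcome ages in 8.4 are untouched. A reader might infer that the whole account of progression would no longer be that of the recruited patients. The protocol does not support that for the outcome ages or for any unfiltered description. Whether the filter reaches the bivariate comparison is unclear: 8.5 describes it separately, while 8.7 also runs linear correlation in bivariate models. This part stands.

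**Leniency.** Read generously, a patient needs only one two-year stretch in a long chart, and irregular charts could often pass. So it cannot be said that every patient without regular annual data is dropped. That limits the size of the loss. It does not rescue single or widely spaced values.

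**Patients unable to travel.** A reader might infer that the filter removes those for whom, as 8.2 puts it, "a collaborator of the main researcher will reach the patients at his residence to recruit him". That does not follow. All data predate the recruitment visit, and a patient who cannot travel now may have been followed regularly before. Likewise, no passage links visit regularity to severity or recruitment source.

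**Rationale.** Two values are a sensible minimum for calculating an individual's own change. A visit rule may also limit the weight of patients seen often because they were unwell, a problem that using all values can worsen. Patient-specific slopes may not be estimable for many variables in at most 33 patients split by genotype. These are fair points, and the fix has to allow for them. They do not justify the filter for correlation with age, which needs neither two values per patient nor annual spacing.

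**Conclusion.** The concern holds for the linear correlation analysis and the multivariate correlation models. As written, the rule discards usable values with known ages from the study's core method, without a stated reason or a check against all data, and it is too ambiguous to be applied in only one way.

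Selection by follow-up pattern follows from the rule itself; bias does not, and may be zero. The retention shares and odds ratios behind the figures are assumptions, so those figures show a plausible scale and are not estimates for this cohort. The point is worth correcting before analysis, but it does not undermine the study as a whole.

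**What to change.** In 8.5, replace the filter with the use of all dated measurements at exact age at evaluation. Analyse them in a model that accounts for repeated values within patient, with a patient-specific intercept and a patient-specific slope where the data support one. Patients with a single value then still inform the mean curve.

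Keep a minimum of two values only where an individual's own slope is calculated, and say that it applies per patient and per variable. Define the yearly-visit subset in unambiguous terms and report it as a sensitivity analysis, which also checks for informative visit timing. State whether any restriction applies to the bivariate comparison.

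The cost is a change of wording and some extra data entry for off-schedule visits. No new patients or procedures are needed. The downside is that visits made when unwell may be over-represented; a clear difference between the all-data and yearly-visit results would be a sign of this.

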8.6 Data management

Data will be managed on a specific database created in an excel file, defended by a password. The file won't include any personal data and patients will be identified through a pseudonym that could be decrypted only through the access to a second file, defended by a different password.

8.7 Data analysis

Analysis will be performed using generalized linear regression models suitable both for continuous variables both for independent ones. Variables with a nonlinear distribution will be transformed in logarithmic scale before the analysis to be performed. For any analysis data will be divided according to the age of the patient at the moment of the evaluation. Data will be analyzed with linear correlation both compared to the variable age both in bivariate models and multivariate models. Results obtained will be adjusted for confounding factors not related to muscular dystrophy.

Data of included patients will be globally studied and divided in two groups homogeneous for genotype.

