8.3 Variables

Will be extract from the clinical charts of these patients, after the sign of the informed consent for the data management, only retrospective data (therefore all those data older than the day of the recruiting visit).

These data will be reported in a excel file specifically created. On this file data will be anonymized through a patient identification code that will be decrypted in another separate file. For this file will be considered the following data:

a) Dati anagrafici:

1. Anonymized name
2. Sex
3. Age

Form 2- DIAGNOSIS:

- 1) Age at onset
- a) clinical presentation
- b) clinical progression
- 2) CK at onset
- 3) EMG

4) Biopsy:

- a) Histology
- b) Immunohistochemistry
- c) Western Blot

5) Genetic:

- a) In frame del/dupl
- b) Out of frame del/dupl
- c) Missense
- d) Nonsense

Form 3- CLINICAL DATA AND TREATMENTS:

Hospitalization: Data – Cause – Frequency* Surgery: Data – Complications* Fractures: Data – Frequency – Location* Fell: Data – Frequency* Emergency Room Accesses: Data – Cause*

APPARATUS

Skeletal-Muscle

1) Clinical tests:

NSAA* MFM* QMT* Brook Scale* Egen Klassifikation* Barthel Index* Walton and Gardner* & Medwin GSGC* Grip Strength (quantitative)* Handheld Dynamometry* Performance of the Upper Limb Module for DMD 2.0* 10m Walk: 1- normal, 2- slightly impaired- 3 moderately impaired- 4- impaired- 5 with device - 6 not walking but stands- 7 wheelchair 6MWT* time to rise from the floor* Climb 4 stairs (1 no help - 2 one hand on the leg – 3 two hands on the legs - 4 stand with help -5 Handrail - 6 hardly climbs- 7 Not able). 10m Run

Time to rise from a chair (1 Normal - 2 with difficulties -3* helping with one hand - 4 Helping with two hands - 5 other helps - 6 Impossible). Time to stand from the floor (1 Normal - 2 first rise the pelvis and then one hand on the floor - 3 First rise the pelvis and then two hands on the floor - 4 One hand on the leg - 5 Two hands on the legs - 6 Other help - 7 Impossible).

Neuromuscular evaluation (date): maximal voluntary strength: bilateral knees extension, Isometric contraction test*, bilateral knee flexion, Workspace volume

2) Exams:

CK* Muscular RMN

3) Symptoms:

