Loss of independent ambulation* Calf hypertrophy (Unilateral/Bilateral, if bilateral → Symmetrical/Asymmetrical)* Calf atrophy: Unilateral/Bilateral, if bilateral → Symmetrical/Asymmetrical)* Tendon contractures* Scoliosis Scapular winging* Tiptoe gait pattern* Muscle pain* Muscular trophism* Muscular weakness (Symmetrical/Asymmetrical - Proximal/Distal - Progression: chronic/acute)* Muscle contractures (Unilateral/Bilateral - site*

Cramps: Severity – Frequency)* Clubfoot (Unilateral/Bilateral)* Spine anomalies* Ability to walk on toes* Fasciculations* Percussion induced muscular contractions* Macroglossia (yes/no)* Dysphagia(yes/no, Data onset, Progression chronic/acute, Severity-> light/moderate/severe, frequent aspirations:yes/no)

4) Muscles involved: shoulder* arms* forearms* hand* spine* pelvic muscles* thigh* leg* feet

5) Wheelchair: yes/no; if yes → changed through the years – still using yes/no – how long*-other ambulatory devices yes/no; if yes → name → still using yes/no – how long – has it been changed through the years?

6) Deambulation and motility: general comments* Electromyography*

Cardiovascular

1) Evaluations (data): general conditions: using devices to support heart function (eg. pacemakers, ICD, etc.) - name* still using? – How long? - has it been changed through the years?

2) Conduction system anomalies:

EKG * Holter EKG* Echocardiogram* events monitoring*

3)Cardiomyopathy* Heart RM*

4) Symptoms: basal rattling* Oedemas* slopes edemas * Holter* Echocardiogram: Description* FE* Left ventricle telediastolic Volume* Left ventricle telediastolic diameter* Ahythmies* Coronaropathy* Valve* Pulmonary hypertension* Palpitations* Syncope* almost syncope*

Respiratory

1) Evaluations (data):

2) Respiratory support: Invasive/ Noninvasive* Cough assist* Cough peak* Overnight BiPAP * Other*

3) Respiratory status* Pulsoxymetry/polysomnography (mean SpO2 - SpO2 minimal - FC mean - AHI – ODI – %* MVV – MIP – MEP. Dispnoea: supine position– stress induced – at rest*

4) Quality of sleep: daily somnolence* not restorative sleep* frequent overnight awakening* morning headaches* daily fatigue*

Laboratory Tests

1)Imaging tests (data): RX thorax* RX spine* RM muscle*

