8.7.1 Primary endpoints: analysis

- To obtain a variables distribution according to patients' age and to verify possible correlations with the disease's progression.
- To study possible correlation between variables identified.
- To evaluate possible connections with clinical outcomes

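### For 6MWT, timed rise from the floor and 10m run, values stop when the ability is lost, so the age correlation in 8.7, read as pooling visits by age, rests at older ages on slow progressors and understates decline

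*Protocol*

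**What the plan says.** Protocol 8.7 fixes the method for all variables: "For any analysis data will be divided according to the age of the patient at the moment of the evaluation", and then "Data will be analyzed with linear correlation both compared to the variable age both in bivariate models and multivariate models". Section 8.7.1 makes this the first primary analysis: "To obtain a variables distribution according to patients' age and to verify possible correlations with the disease's progression". Section 8.5 limits the input: "Only data corresponding to yearly visit (at least two data in two years) will be used for the linear correlation analysis". The expected cohort is 33 patients.

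The form in 8.3 treats inability in two ways. The graded 10m walk ends in codes for non-walkers, and the next two entries have none: "6 not walking but stands- 7 wheelchair 6MWT* time to rise from the floor". Likewise the stair item has a code for inability, while the run listed after it has none: "6 hardly climbs- 7 Not able). 10m Run". The graded chair and floor items also end in a code for impossible (6 and 7).

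The form records "Loss of independent ambulation" as a symptom, and 8.4 makes the age at which it happens one of three clinical outcomes. The protocol therefore expects patients to stop walking during the period covered by the charts. Neither 8.7 nor the limitations in 8.9 connects this with the age analysis of the three tests.

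**The concern.** A patient who loses ambulation early leaves the 6MWT data early. At older ages the remaining values come from patients who lose ambulation late and have therefore declined slowly. A line fitted through all available values against age mixes two things: patients getting worse, and the worst patients leaving. The second flattens the line.

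Describing natural history and finding the variables most strongly related to evolution are primary endpoints (8.1.1). Section 8.7.2 would use the results to choose follow-up variables and possibly to drop examinations as useless. A test whose age correlation is weakened because fast progressors have left could be ranked too low, and a decline rate quoted from the pooled line would be too slow for later use.

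**Working it through.** The protocol states no rate of decline, age at loss or 6MWT level, so it has no figure to reproduce. The check is whether the stated method recovers a known decline.

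**Hand illustration.** Assume 6MWT is 420 m at age 6 and falls linearly to 120 m at the patient's own age at loss L. The yearly loss is (420 − 120)/(L − 6).
- Patient A, L = 12: 300/6 = 50 m/year. At age 11: 420 − 5 × 50 = 170 m. No value from age 12.
- Patient B, L = 20: 300/14 = 21.4 m/year. At age 11: 420 − 5 × 21.4 = 313 m. At age 13: 420 − 7 × 21.4 = 270 m.
- Mean of available values: (170 + 313)/2 = 241 m at age 11, and 270 m at age 13.

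Both patients decline, yet the mean by age rises.

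**Simulation.** From the protocol: 33 patients (8.5), yearly visits (8.5), linear relation with age (8.7). Assumed: visits from age 6, current age 8 to 40, the 420 to 120 m line above, noise SD 30 m, and four settings for age at loss. Slopes are in m/year. The shortfall is 1 − pooled slope/median patient slope.

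| Mean (SD) age at loss, years | Median patient | Pooled on age, walkers only | Shortfall | Pooled, non-walkers as 0 m | Within-patient while ambulant |
|---|---|---|---|---|---|
| 14 (3) | −37.8 | −26.7 | 29% | −14.7 | −38.0 |
| 16 (5) | −30.4 | −18.5 | 39% | −15.3 | −30.6 |
| 18 (6) | −25.1 | −15.5 | 38% | −15.5 | −25.3 |
| 20 (8) | −22.0 | −12.9 | 41% | −15.0 | −22.4 |

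First row: 1 − 26.7/37.8 = 0.29.

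Zero coding is worse than leaving non-walkers out in two settings, equal in one and slightly better in one, because the floor at 0 also flattens a straight line. The within-patient slope recovers the decline in all four.

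**Second set of assumptions.** Mean age at loss 12, 15 or 20 years, SD 2 to 8, 6MWT from 450 m at age 5 to 100 m at loss, eight yearly visits per patient. In all six settings the pooled slope was too shallow, at 41 to 67% of the median patient's decline (a shortfall of 33 to 59%). The within-patient slope recovered 89 to 99%, and the zero-coded line 25 to 87%. Past the mean age at loss only about 7 to 10 of the 33 patients still gave values, and their own loss came about 2 to 7 years later than the cohort mean.

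The simulations cover 6MWT only. For the timed rise and the run the mechanism and direction are the same, but no size was computed.

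**The case against.** A reader might infer that all walking-based tests stop producing values. The form does not support that: the graded 10m walk, stairs, chair and floor items keep a code for patients who cannot do them. Only three entries are affected, on a form that also holds upper-limb, strength, respiratory and cardiac measures. Nothing in the protocol calls these three the main motor tests.

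A reader might also infer that the protocol excludes visits after loss of ambulation. It does not say so. How an unable result is coded is commonly left to an analysis plan or data dictionary, and a missing coding rule alone would be no finding. Nor does 8.7 say outright that visits are pooled across patients; pooling is the natural reading, not the only one. This limits the point but does not remove it. Section 8.7 commits every analysis to division by age and linear correlation with age, and under that method neither blanks nor zeros give the right slope.

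A third tempting reading is that variables are always compared on different patients. The bivariate comparison in 8.5 couples two variables and so needs both values at the same visit. The problem arises only when separate age correlations are ranked against each other.

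Finally, loss of ambulation is not ignored: its age is an outcome (8.4), and 8.7.1 relates variables to outcomes. But that is a separate analysis and leaves the age slopes uncorrected.

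**Conclusion.** The point holds for 6MWT, timed rise from the floor and 10m run, with 8.7 read as pooling visits by age at evaluation. The direction, decline understated, was the same in every setting tried. The size is illustrative only: about 30 to 40% under the first set of assumptions and 33 to 59% under the second. Neither range can be quoted as the bias in this cohort, because the ages at loss, the 6MWT levels, the noise and the visit pattern are all assumed. It is worth correcting because the affected analysis is primary and the remedy uses data already collected. It does not undermine the graded items or the paired comparisons.

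**What to change.** In 8.7, for these three tests only:
- Estimate decline as within-patient change while ambulant, for example with patient-specific slopes or a mixed model with random slopes. Report it beside age at loss of ambulation.
- When describing values by age, show at each age the proportion no longer able to do the test, next to the values among those still able. Do not fit one straight line with non-walkers coded as 0.
- When ranking variables by their separate correlations with age, compare them on the same patient-visits.

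The cost is a few sentences and slightly more analysis work. Loss of ambulation and wheelchair use are already extracted. The downside is that slopes will be imprecise for patients with few ambulant visits, which matters in a cohort of about 33.
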